2.2 Previous Data

Our preliminary data includes a retrospective analysis of national claims data; we compared narcotic use in 706,863 women with endometriosis with age- and region-matched controls without endometriosis. In the two years following the diagnosis of endometriosis, 56.3% of women with endometriosis had filled a prescription for narcotic pain medication as compared to 34.5% of the controls over a similar two-year time frame (manuscript in preparation). It is critical that we find non-narcotic alternatives to symptom management for this group of women suffering during what should be the peak of their productive years of life. We do not have preliminary data specific to the use of LDN. The results of this study would potentially serve as preliminary data for future large-scale multi-center studies. There is sufficient preliminary data (for alternative disease states) in the existing literature regarding the safety and potential efficacy of LDN to support the further study of LDN. These studies are also discussed in more detail in the background section of the protocol.

2.3 Study Rationale

Naltrexone hydrochloride is a well-known, competitive opioid antagonist traditionally used to treat opioid overdose or addiction. At much lower doses, naltrexone has significantly different pharmacologic properties. Low-dose naltrexone (LDN) acts on non-opioid receptors in the central nervous system to decrease activation of microglial cells and decrease plasma levels of multiple inflammatory cytokines. LDN has also been shown to transiently block all three subtypes of opioid receptors (μ , κ , δ) resulting in an upregulation of not only opioid receptors, but also increasing endogenous opioid production. Early studies of LND in other inflammatory disorders, such as inflammatory bowel disease and fibromyalgia, have demonstrated promising results. Since the pelvic pain associated with endometriosis is due in part

to increased peritoneal inflammation, LND has the potential to provide non-narcotic analgesic relief by decreasing endometriosis-associated inflammation.

3.0 Inclusion and Exclusion Criteria

3.1 Inclusion Criteria

Inclusion

- Premenopausal female ages 18 to 45 years old on the day of signing informed consent.
- Must agree to use only study-specific analgesic medications during the study and is not known to be intolerant to them.
- Diagnosed with endometriosis and has had, within the last 10 years prior to signing the informed consent, surgical diagnosis with direct visualization and/or histopathologic confirmation of endometriosis.
- Is not expected to undergo gynecological surgery or other surgical procedures for treatment of endometriosis during the study period.
- Agrees to use contraception if not surgically sterile during the entire study.
- Patients using oral contraceptives, LARCs and/or GnRH agonists/antagonists for contraception and/or management of endometriosis, with a stable regimen, will be able to continue in the study, however, women using oral contraceptives and GnRH agonist/antagonists will be switched to Norethindrone acetate during the 1-2 week run-in period as prescribed by principle investigator.

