4.4 Eligibility/screening of subjects

When the study team receives information about a potential subject, follow-up is made to verify eligibility. If excluded, no further questions are asked and they are thanked for their time. If eligible the subject is scheduled for a visit.

Follow-up includes a phone screen of the potential subject by asking questions such as, ensuring the subject is premenopausal and in between the ages of 18 and 45 years old, agree to only use study-specific analgesic medications during the study and if intolerance to oxycodone and ibuprofen are known, agrees to use Norethindrone acetate and either their LARC or other barrier contraception while in the study, if the subject plans on becoming pregnant or trying to conceive at any point during the study, if the subject has any chronic daily narcotic use and any chronic pain other than endometriosis, and verify the subject is able to speak and read English to answer the surveys. We will also confirm that the subject is willing and able to be reliably contacted by email for study specific purposes.

If the participant passes the phone screen, the participant will be scheduled for a screening visit. After consent and receiving Norethindrone acetate, an email will be sent for the subject to complete the daily surveys for next 6-7 days. Upon completion of the surveys, the participant will pass or fail the screening process.

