7.0 Study Design and Procedures

7.1 Study Design

We propose to conduct a randomized double-blind placebo-controlled trial to evaluate the effectiveness of low-dose naltrexone (4.5 mg daily) in combination with a standard treatment (norethindrone acetate daily) on management of endometriosis-associated pain. Potential subjects will be screened in the Penn State Minimally Invasive GYN Surgery clinic for endometriosis-associated pain for greater than 6 months. Subjects will be screened from new and existing patients in the Minimally Invasive GYN Surgery clinic as well as from referral sites including surrounding general OBGYN and Primary Care practices. Those meeting all inclusion and exclusion criteria that are willing to participate will receive a detailed history and physical exam. Baseline survey data will be collected and entered into the RedCap secured database. At this time subjects will be set up for daily emails to complete VAS scores directly into RedCap. The first visit will be scheduled 1 week following the screening visit.

During the first visit subjects will be screened for daily reporting compliance. Subjects having completed 5 or fewer daily VAS scores and surveys during the baseline collection will be offered one additional 7-day period to improve compliance. If at the conclusion of the second 7-day run-in period of gathering daily baseline VAS scores and survey responses they continue to have 5 or fewer entries per week they will be considered a screen failure and withdrawn from the study. Those subjects meeting the 6 entry or more threshold of daily reporting at either visit 1 or following the second 7 day run in period will be randomized in the study.

Randomized subjects will receive norethindrone acetate 5 mg (up to 15 mg depending on subject's needs) daily plus LDN 4.5 mg daily or norethindrone acetate 5 mg (up to 15 mg) daily plus placebo. If the subject is taking norethindrone acetate prior to the study, she will remain on her current dose to start the study. Dose adjustments will be made, if needed, to achieve amenorrhea or minimize uterine bleeding. Menstrual status will be assessed and documented in a progress note if this should occur either in person at a study visit or via telephone in the interim. Norethindrone acetate is provided in 5mg tablets; if dosing adjustment is needed, the study staff will arrange to ship additional study drug via FedEx.

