Pre-screening will take place over the phone with women identified as potential candidates for study participation via clinic visits or other previously discussed methods of subject recruitment. Initial contact will be made via the telephone to assess women's interest in participation. As per standard of care, narcotic usage is assessed during routine clinic visits.

If the subject meets all pre-screening criteria, the subject will be scheduled for a screening visit. At the screening visit, the informed consent will be reviewed and the subject will be given ample time to ask any questions or concerns about the study. Once informed consent is signed, the subject information will be placed in redcap and a test email will be sent to the subject. Those meeting all inclusion and exclusion criteria that are willing to participate will receive a detailed past medical history and physical exam. Baseline surveys and any adverse events will be collected and entered into the RedCap secured database.

The subject will complete the WERF survey, VAS score, EHP-30 and PGAs during the visit to ensure understanding and allow the coordinator to help with any questions. The subject will be given a 2 week supply of Norethindrone acetate to start during the run-in period and given instruction on how to complete the daily VAS scores and study questions. It will be explained to the subject that they must complete at least 6 out of the 7 days of surveys to be enrolled into the study. If the subject is unable to complete the 6 out of 7 days of surveys, the subject will be given one additional week to determine if compliance is attainable. (This will ensure provide ample opportunity for

enrollment for potential subjects with unpredictable barriers to completion in the first 7 days.) If the subject is unable to do so, they will be a screen fail. Those completing greater than or equal to 6 entries in either of the 7-day periods will be eligible for enrollment in the study. In the event of needing an additional 7-day run-in period, data points during the screening period will **not** be assessed in aggregate for eligibility.

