7.4.3 Method for Assigning Subject to Treatment Groups

Randomization is a critical feature of a clinical trial because it prevents treatment-selection biases. The statistician involved in this study will develop the programs necessary for the random number generator to create the randomization; however, the final random seeds used to generate the randomization scheme will be prepared by a statistician in PSU's Department of Public Health Sciences independent of the study in order to keep this study's statisticians blinded as well. The randomization scheme for this study will use variable-size, random permuted blocks to ensure that ensure the number of participants in each treatment arm. IDS will be performing randomization to ensure proper blinding of the study team. They will also be responsible for distributing the study medications according to assigned group as per there standard operating procedure.

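### New versus established norethindrone acetate use is a plausible baseline predictor of 12-week pain that the VAS models leave out; adjusting for it is a cheap gain in precision, not the cure of a bias

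*Combined protocol and SAP*

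**What the plan says.** Section 3.1 (Inclusion Criteria) says of users of oral contraceptives, LARCs or GnRH agents: "with a stable regimen, will be able to continue in the study, however, women using oral contraceptives and GnRH agonist/antagonists will be switched". It does not define how long stability must have lasted. The drug they change to is norethindrone acetate, and the change is made in the run-in of one to two weeks.

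Section 7.2.1 (Screening visit) describes the start of the background drug: "The subject will be given a 2 week supply of Norethindrone acetate to start during the run-in period". The visit table in 7.1 marks this dispensing as applying only where needed. Randomisation follows soon after: "The first visit will be scheduled 1 week following the screening visit" (7.1), with one further 7-day run-in allowed for women who report too few diary entries.

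Established users are handled differently. Section 7.1 states: "If the subject is taking norethindrone acetate prior to the study, she will remain on her current dose to start the study". LARC users take both treatments: the phone screen in 4.4 asks that the woman "agrees to use Norethindrone acetate and either their LARC or other barrier contraception while in the study". A LARC user not already on norethindrone acetate is therefore a new starter too.

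Section 7.4.3 gives the allocation method: "The randomization scheme for this study will use variable-size, random permuted blocks". It names no stratification factor. In Section 8.3 the primary model has treatment group and one covariate, opioid intake over the 12 weeks. Neither prior regimen nor run-in VAS is in it. Run-in VAS appears only in a secondary model, as one level of the time factor, and contrasts within and between arms are taken from that model. No analysis by prior regimen is described.

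**The concern.** The protocol treats norethindrone acetate as standard treatment for endometriosis and allows its dose to be adjusted after randomisation according to bleeding. A woman 7 to 14 days into it may still be responding to it during the 12 weeks over which the primary outcome accrues; an established user is more likely to be settled. If so, new versus established use predicts the outcome, and it can be known for every woman before she is randomised. The primary model omits it while adjusting for a variable measured after randomisation.

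Run-in VAS may not fully stand in for this factor. For switched women it is recorded during the switch, before much of any effect of the new background drug could show.

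Two things are at stake. The first is precision: any part of the variance in pain that this factor explains stays in the error term. The second is the reading of within-arm changes from run-in in the secondary model. Among new starters these combine the effect of LDN or placebo with the effect of starting norethindrone acetate.

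**Working it through.** **Inputs from Section 8.2:** difference 10 mm, SD 20 mm, two-sided 0.05, 80% power, 20% withdrawal, 80 randomised per arm.

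**Inputs not in the documents, so assumed:** share of new starters p = 30-70%; difference D in mean 12-week VAS between new starters and established users = 5, 10 or 20 mm. The 20 mm SD is taken as the total SD, including variation due to this factor.

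**Step 1. The plan's own figure.** Per arm, n = 2 × (1.960 + 0.842)² × (20/10)² = 62.8, so 63. Divided by 0.8 this is 79 per arm, 158 in total. The t-test version gives 64 per arm, and 64/0.8 = 80, exactly the stated 160. Power with 64 completers per arm is 80.7% (normal approximation). The sample size reproduces.

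**Step 2. Variance explained.** Share = p(1−p)D²/400. The product p(1−p) is 0.21 at p = 30% or 70% and 0.25 at 50%. Residual SD = 20 × √(1 − share). Equivalent extra patients = 1/(1 − share) − 1. Power at 64 per arm = Φ(10/(residual SD × √(2/64)) − 1.96).

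| D (mm) | Share of variance | Residual SD (mm) | Equivalent extra patients | Power (80.7% unadjusted) |
|---|---|---|---|---|
| 5 | 1.3-1.6% | 19.9-19.8 | 1.3-1.6% | 81% |
| 10 | 5.3-6.3% | 19.5-19.4 | 5.5-6.7% | 83% |
| 20 | 21-25% | 17.8-17.3 | 27-33% | 89-90% |

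For example, at D = 20 and p = 30%: share = 0.21 × 400/400 = 0.21; residual SD = 20 × √0.79 = 17.78; extra patients = 1/0.79 − 1 = 26.6%; power = Φ(3.18 − 1.96) = 0.889. With p at 25% or 75%, power at D = 20 is 88%.

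**Step 3. What chance imbalance contributes.** With 80 per arm, ignoring blocking, the SD of the between-arm difference in the share of new starters is √(2p(1−p)/80) = 0.072 to 0.079. Multiplied by 1.96 and by D, the 95% range of the resulting shift is about ±1.4 to ±1.5 mm at D = 10 and ±2.8 to ±3.1 mm at D = 20.

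The unadjusted standard error is 20 × √(2/80) = 3.16 mm, a 95% half-width of 6.2 mm. The shift is already part of that 6.2 mm. It combines with the rest as squares: at D = 10 and p = 30%, 6.03² + 1.42² = 38.4 = 6.20². Adjustment narrows the half-width to about 6.0 mm at D = 10 and to 5.4-5.5 mm at D = 20.

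**The case against.** A reader might infer that the mix of new and established users biases the LDN comparison. It does not. Both arms receive norethindrone acetate, randomisation balances prior use in expectation, and the 5% test already allows for chance imbalance. For the same reason the shifts in Step 3 must not be read as an error on top of the stated confidence interval. This part of the objection stands in full.

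The size is also open to challenge. Nothing in the documents says how many women will be new starters, or that the factor is among the strongest predictors of pain. Switched women come from other hormonal regimens rather than from no treatment, both groups have their dose adjusted toward the same bleeding goal, and established users who still want a pain trial may have as much pain or more. The two-level factor also pools women with different histories. So neither the size nor the direction of D is known, and the gain is large only at the 20 mm end. This stands too. What remains is that the factor is plausible, and that including it costs one degree of freedom.

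A reader might conclude that the blocks must be stratified. At 160 women, adjusting without stratifying loses only about 1/160 in efficiency on average, so nearly all the gain comes from the covariate. Part of it might also be obtained from run-in VAS if that were added.

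Finally, 3.1 might be read as contradicting itself. Its wording introduces the switch as an exception, and stability can describe the regimen at entry. The sentence needs clarifying, but it does not amount to a demonstrated error.

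**Conclusion.** The point holds as a modest, nearly free improvement in precision. The documents show that both established and newly started users are randomised, and that neither the allocation nor the primary VAS model takes account of it. The between-arm comparison remains valid and N = 160 need not change.

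On the assumptions above, the gain is negligible at a 5 mm difference, small at 10 mm and material only at 20 mm, a difference as large as the whole planning SD. These figures also assume that no other baseline covariate already absorbs the same variation.

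Within-arm changes from run-in, which arise only in the secondary model, should not be read as the effect of LDN or of placebo alone. Any within-arm change is already a mixture; here the start of norethindrone acetate is a further, identifiable part of it. Adjustment for the factor does not remove this.

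**What to change.** In Section 8.3, pre-specify before unblinding a two-level baseline covariate in the VAS models: norethindrone acetate established before screening, versus newly started or switched at screening. Count LARC users who add it as newly started. State that within-arm contrasts from run-in include the effect of starting norethindrone acetate.

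The data need is small. Past medical history is taken at screening, and 7.4.6.5 has concomitant medications documented. The screening form should make sure that the prior hormonal regimen and the norethindrone acetate start date are captured explicitly.

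Stratifying the blocks in 7.4.3 on the same factor is optional; it adds some pharmacy administration and little beyond adjustment. Women already randomised cannot be restratified but can be adjusted for.

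The investigators should reconcile the stability wording in 3.1 with the run-in switch, so that it is clear to whom, and at what time, the condition applies. No eligibility or clinical rule is proposed here.

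The total cost is one degree of freedom, a sentence or two in 8.3, a check of the screening form and a clarification in 3.1.

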3.2 Exclusion Criteria

Exclusion

- Women that are pregnant, breastfeeding or trying to conceive.
- Patients with chronic daily opioid use and any chronic pain or frequently reoccurring pain condition, other than endometriosis, that is treated with opioids or requires analgesics for more than 7 days per month.
- Patients with abnormal liver function tests (greater than 3x normal limit) in the past year or history of liver disease. Routine screening of liver function is not required.
- Non-English speaking or inability to read and understand English secondary, in part, to the need to read and report daily results in English.
- Undiagnosed vaginal bleeding
- Patients with history of opioid, illicit drug or alcohol abuse
- Patients currently taking thioridazine
- Patients with a history of suicidality
- Patients with current or history of unstable depression or other psychiatric disorder who, by PI judgement, are unstable or not well controlled
- Known, suspected or history of cancer of the breast
- Active deep vein thrombosis, pulmonary embolism or history of these conditions
- Active or recent arterial thromboembolic disease (e.g., stroke, myocardial infarction)

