3.3 Early Withdrawal of Subjects

3.3.1 Criteria for removal from study

Subjects will be removed from the study for safety reasons. Subjects will be evaluated for potential negative reactions to study medications at each visit. Additionally, subjects will be advised to contact the study team with any new negative symptoms to arrange evaluation.

Additionally, unintended pregnancy during the study period will meet criteria for withdrawal from the study.

Withdraw of consent at any time during the study period will also constitute the withdrawal of study subjects.

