The study will include a 12-week intervention period during which subjects will be asked to record daily electronic VAS scores, report daily analgesic use (NSAIDs and opioids) and complete surveys every 4 weeks. VAS scores will be reported daily. Patient Global Impression of Change (PGIC), Patient Global Assessments (for pain, dysmenorrhea, nonmenstrual pelvic pain and function) (PGAs) and Endometriosis Health Profile-30 (EHP 30) surveys will be completed at 4-week intervals during the intervention (0, 4, 8, and 12 weeks). Subjects will be asked to complete a brief telephone interview visit at 16 weeks to complete final quality of life surveys (EHP 30, PGAs and PGIC).

Subjects will be screened for side effects and asked to record pain medication use throughout the duration of the study. Subjects will be dispensed a 4-week supply of medications from the Investigational Pharmacy. They will be required to bring medication bottles to each visit for counting and drug accountability. Any remaining capsules will be returned to the pharmacy. All study subjects and investigators will remain blinded to the study group until the completion of the study. In the event subjects cannot attend study visits in-person due to extenuating circumstances (e.g. related to COVID-19 pandemic), remote visits can be completed via telephone for which questionnaires will be sent via REDcap and IDS will ship of study drug. Drug accountability and monitoring for side effects can also be done via telephone.

Procedure	Pre- screen	Screening Visit (beginning of Run-in week)	Visit 1 Enrollment – Randomization (Day 1)	Visit 2* 4-weeks (Day 28- 30)	Visit 3* 8-weeks (Day 56- 58)	Visit 4* 12-weeks (Day 84- 86)	Visit 5 16-weeks Phone f/u (Day 114- 121
Screening Criteria	Х						
Informed Consent		X					
WERF Questionnaire		Х					
Physical		Х					
Past Medical History		Х					
EHP-30		Х	Х	Х	Х	Х	Х
PGIC				X	X	X	Х
PGAs		Х	Х	Х	X	Х	Х
Study Drug Dispensed & Compliance		X (Only Norethindrone Acetate given, if needed)	Х	Х	Х	Х	
Daily Pain, Analgesic and Study Medication Assessment		X (6-7 days)	X (Daily)	X (Daily)	X (Daily)	X (Daily)	X (Daily)
Screening/Assessment of Adverse Events		X	Х	X	X	X	Х

Visit Table Summary of Study Procedures

(*) - these asterisked visits can be done remotely via telephone, if warranted due to extenuating circumstances.

7.2.1 Screening visit:

Screening Visit 1:

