13.0 Sharing Results with Subjects

There is no information for the patient to receive as no diagnostics will be done.

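### Pregnancy is an exclusion, but no pregnancy test is scheduled before norethindrone acetate at screening or before the first study-drug dose at Visit 1

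*Combined protocol and SAP*

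**What the plan says.** Section 3.1 enrols premenopausal women aged 18 to 45 and requires those who are not surgically sterile to agree to contraception for the whole study. Section 3.2 excludes "Women that are pregnant, breastfeeding or trying to conceive". It names no method for checking this.

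The phone pre-screen in 4.4 asks "if the subject plans on becoming pregnant or trying to conceive at any point during the study". The questions in 4.4 and 5.1.2 are given as examples, so a question about current pregnancy may also be asked.

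The screening visit (7.2.1) consists of consent, medical history, physical exam, questionnaires and adverse-event recording. Norethindrone acetate for two weeks is then handed out; the visit table qualifies this as "Only Norethindrone Acetate given, if needed". Section 4.4 places dispensing ahead of the run-in result: "After consent and receiving Norethindrone acetate, an email will be sent for the subject to complete the daily surveys". At Visit 1 (7.2.2) the woman is randomised if she meets all criteria, and takes her first dose of study drug in clinic.

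The visit table has no pregnancy-test row, and the descriptions of Visits 1 to 4 and the follow-up call mention no test.

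**The concern.** An exclusion protects only as far as it can be checked before dosing. Here every check depends on the woman's own knowledge or on an examination that cannot be relied on to show an early pregnancy. Agreeing to use contraception from now on does not show that she is not already pregnant.

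Self-recognition may also be less dependable in these women. Under 3.1 and 7.1 some will arrive on oral contraceptives, long-acting methods, GnRH agents or norethindrone acetate. It is a fair inference, though not stated, that some have no regular period to miss. Section 11.0 lists nausea and breast tenderness among the common reactions to norethindrone, so early signs during the run-in could be put down to the drug.

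At stake is the dosing of a woman whom the protocol means to keep out, first with norethindrone acetate and then with study drug. This is a matter of safety and eligibility checking, not of the statistical analysis.

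**Working it through.** **1. Checks and exposures, side by side**

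| Stage | Bearing on pregnancy | What she may be given |
|---|---|---|
| Phone pre-screen (4.4, 5.1.2) | Question on plans to conceive; others possible | Nothing |
| Screening visit (7.2.1, visit table) | History, physical exam; no test | Norethindrone acetate for two weeks, where needed |
| Visit 1 (7.2.2, visit table) | All criteria must be met; no test | First study-drug dose in clinic, plus one-month supplies |

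No row contains a check that would reliably find a pregnancy the woman does not know about.

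**2. How many women are concerned (upper bounds)**

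Inputs from 8.1: target of 160 randomised, 50% screen failure, 320 to 350 screened.

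- Plan's own figure: 160 / (1 − 0.50) = 320, the lower end of the stated range. The upper end implies a failure share of (350 − 160) / 350 = 54.3%; the plan does not explain the difference.
- Women who could be given norethindrone acetate at screening: up to 320 to 350.
- Of these, not randomised: 320 − 160 = 160, to 350 − 160 = 190. This assumes that every failure happens after dispensing and that every woman needs a supply.
- Women who take study drug or placebo: 160, for up to 12 weeks (7.4.2).

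The number dosed while pregnant would be the number dosed times the share with an unrecognised pregnancy. The documents do not give that share, so the product is left uncalculated.

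**3. Number of tests the remedy needs**

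Two tests for each randomised woman and one for each woman who fails the run-in:

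- Lower: 2 × 160 + 160 = 480.
- Upper: 2 × 160 + 190 = 510.

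This assumes that no woman is surgically sterile and that all 320 to 350 reach the screening visit.

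**4. Effect on the statistical plan**

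Inputs from 8.2: standardised effect 0.5, two-sided alpha 0.05, power 80%, withdrawal 20%. A two-sample t-test needs 63.8, so 64 per arm; 64 / 0.80 = 80 per arm, or 160 in all, as stated. The normal approximation gives 63 per arm; 63 / 0.80 rounds up to 79, or 158. None of these inputs changes if a test is added before randomisation. A positive result adds to the number screened, not to the number randomised.

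**The case against.** The best case for the plan is that it already has several layers: women trying to conceive are excluded, contraception is required, undiagnosed vaginal bleeding is an exclusion, a history and physical exam are done, and the site must confirm all criteria before randomising. A clinic may also test as routine care, and a test could be mentioned in pages that are not in the public document. The risk section names no embryo-fetal risk for either drug. All of this stands, and it lowers the likelihood and the weight of the point. It does not put a test into the schedule that staff will follow.

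A reader might infer more than the documents support, in four ways.

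- **That testing was ruled out.** Section 13.0 says "There is no information for the patient to receive as no diagnostics will be done", but that sentence explains why there are no results to share; it does not set eligibility procedures. Section 19.2 provides for abnormal test findings. The express waiver for liver tests in 3.2, "Routine screening of liver function is not required", does not show that pregnancy testing was considered and rejected; other exclusions are also silent on method.
- **That detection of pregnancy during treatment is the defect to be repaired here.** Section 3.3.1 says that "unintended pregnancy during the study period will meet criteria for withdrawal from the study", and how such a pregnancy would be noticed is a separate question. Two tests at entry do not answer it.
- **That 160 to 190 women will be exposed in the run-in and then fail.** The supply is given only where needed, women already on norethindrone acetate keep their dose, and 8.1 reports failure rates below 10% in sister studies without the reporting rule, so some failures may precede dispensing.
- **That a count of harms follows.** Without a pregnancy rate, it does not.

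**Conclusion.** The point holds for entry to the trial. Followed as written, the plan can give norethindrone acetate, and then study drug, to a woman with an unrecognised early pregnancy whom section 3.2 excludes. This goes beyond a missing detail, because the listed checks cannot reliably find such a pregnancy.

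Its size can be stated only as a ceiling on women dosed without a test, as worked out above. The true numbers are lower by the surgically sterile share, which is not stated, and for the run-in also by women who need no new supply. The count of run-in failures exposed is an assumption, not a finding. Confidence is medium, since testing may take place outside the documents. The trial's inference is untouched; this is a cheap safety improvement that should be made.

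**What to change.** For women who are not surgically sterile, add a urine pregnancy test to the visit table and to 7.2.1 and 7.2.2 at two points:

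- at the screening visit, before norethindrone acetate is given;
- at Visit 1, once run-in reporting has been passed and before randomisation, hence before the first study-drug dose.

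Require a negative result to proceed. Treat a positive result as a screen failure, stop any run-in norethindrone acetate, and tell the woman her result. Edit 13.0 to match, since there would then be a result to share. State that the tests cover entry only and do not detect a pregnancy that begins after Visit 1.

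The cost is the tests counted above, at most 480 to 510, plus short text changes. No extra visit is needed: the table's note that "these asterisked visits can be done remotely via telephone, if warranted due to extenuating circumstances" applies to Visits 2 to 4, not to screening or Visit 1. If the site already tests as routine, the change is a table row and a few sentences.
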